[figure not shown]
186 inventories, neuropsychological tests and physical assessments. Three accelerometer calls are
187 administered by two research assistants, for the purpose of giving instructions and answering
188 questions about accelerometers. The estimated overall participation time is 16 hours, which may
189 vary across individuals. To minimize attrition, each assessment session (i.e., T1, T2, T3, T4) is
190 self-paced and has been divided into smaller visits, each of which lasts no longer than 2 hours.
191 During each visit, participants take breaks every 20 minutes to minimize the risk of fatigue.
192

193 ***Daily messaging***

194

195 The 4-week intervention consists of daily messages via email using the online software
196 oTree, an open-source platform for implementing messaging survey, which allows for
197 accessibility via desktop or smartphone [29]. Unique links are assigned each participant at
198 enrollment.

199 Each day, all participants receive daily messages. Participants will be asked to rank 8
200 core values based on personal importance (i.e., politics, religion, family and friends, creativity,
201 money, independence, humor, and spontaneity) during baseline assessment (T1). Participants in
202 the intervention group receive daily prompts to reflect on their highest-ranked core value vividly
203 (e.g., think of a time when you are inspired by your family) followed by a gain-framed message
204 about being physically active (e.g., walking is good for your health). The control group will
205 receive daily prompts to reflect on an everyday activity (e.g., think of a time when you charge
206 your phone) as well as the same content of daily messages but in a loss-framed way (e.g., being
207 sedentary is harmful to your health). These daily self-affirmation and health messages will
208 consist of a combination of the same messages used in the fMRI tasks and novel messages. The
209 Walk-BEST Workbook, a guideline to improve walking safely and effectively
210 (<https://physiobiometrics.com/>), has been used as a reference source of health messages. At the
211 same time, participants will be tested on their memory for health messages from the fMRI task.
212 The participant will then rate their mood and confidence in implementing the health tips, the goal
213 of which is to examine the changing of well-being and self-efficacy of physical activity

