214 throughout the intervention. During weeks 3 and 6, they also receive daily reminders to continue
215 wearing their accelerometers. This daily message survey setup is displayed in Figure 2. The
216 researcher's contact information is displayed on each survey page to enhance compliance. To
217 monitor the participation adherence, participants' responses are tracked and those that do not
218 complete the survey by a specified time of day are contacted the following day by research
219 assistants to prevent technical failures. The time spent on the daily message intervention
220 including the healthy messages and survey questions is recorded by the daily message system, no
221 response to the survey questions or responses under 3 seconds to the self-affirmation probe are
222 considered as non-compliance.

223
224 **Figure 2.** Messaging system setup and logic. Each participant (represented by P_x , where x designates the
225 participant number) receives their unique link. In that link, they follow a series of pages each day that
226 contains their unique questions and parameters based upon the inputted comma-separated values (CSV)
227 file. The system does not initiate until the participant begins on their first day and then repeats for 42 days
228 (4 weeks) for the duration of the daily messaging intervention. The process occurs synonymously for all
229 other participants. Links that are not activated simply remain idle until a participant is assigned that link
230

231 Measurements and materials

233 Physical activity monitoring

234 Time spent sedentary as the primary outcome will be measured with an activPAL
235 inclinometer (activPAL, PAL Technologies, Glasgow, UK). Sleep quality, duration, and physical
236 activity engagement will be measured as secondary outcomes using an GT9X Link
237 accelerometer (ActiGraph LLC, Pensacola, FL). Participants will be wearing two motion sensors
238 at week 0 (between T1 and T2), week 3 (mid-intervention), week 6 (between T3 and T4) and
239 week 14 (T5), 24 hours/day for seven continuous days (see Figure 1). To measure sedentary
240 time, an activPAL monitor is attached on the mid-anterior surface of the right thigh. This device
241 is used to measure postural aspects of sedentary behavior, including time spent lying and sitting,
242 standing, and the number of sit-to-stand transitions. An accelerometer will be worn on the non-

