243 dominant wrist to improve compliance and allow for the assessment of sleep characteristics.
244 Total time spent in physical activity, as well as time spent in light, moderate and vigorous
245 intensities, are measured. Sitting and standing time as measured with an activPAL correlate
246 highly with the direct observation (the gold standard) in classifying sitting and standing in older
247 adults ($rs \geq .95$) [30]. ActiGraph accelerometers can reliably estimate daily physical activity
248 based on a minimum of 4 valid days of wear (i.e., 70-80%) [31] and physical activity energy
249 expenditure as assessed against a gold standard (i.e., doubly labeled water; $rs = [0.34-0.64]$) [32].
250 ActivPAL can reliably estimate sedentary time based on a minimum of 5 days of wear [33]. The

251 use of both devices affords accurate and sensitive measures of both sedentary behavior and
252 physical activity. Participants are also asked to complete a sleep log and record times when they
253 remove and replace the devices during each day (e.g., before and after taking shower). Sleep
254 parameters will be captured through ActiGraph accelerometers.

255 To ensure compliance, there is a conference call prior to each of the three accelerometer
256 weeks, during which the participants will be instructed how to wear the devices correctly.
257 Tutorials for wearing devices are sent out prior to the meeting. During these weeks, participants
258 also receive accelerometer reminders each day at the end of the health message intervention
259 survey and they are instructed to respond to question of whether they are wearing the devices on
260 that day (see Figure 2). A research assistant will reach out if they respond no or do not respond,
261 to prevent any technical issue.

262

263 **Data management**

264

265 All research data are de-identified and only the research coordinator has access to
266 identifiable information that is stored in a secure location. Data are stored electronically on
267 password-protected servers behind university-protected firewalls. All pen and paper inventories
268 and neuropsychological assessments are scored and uploaded to REDCap[70]. Computerized
269 neurobehavioral inventories are collected directly in REDCap and computerized
270 neuropsychological assessments are uploaded to REDCap. (3) The oTree library is used to
271 distribute the daily intervention messages and collect survey data. This system runs on a Heroku

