272 server, a cloud-based system that sends and receives hash-encrypted links. Collected anonymized
273 data are stored on the messaging site behind an administrative login on the Heroku server.

274

275 *Analysis plan*

276

277 Power calculations were performed to statistically determine the target sample size of
278 N=80 for this pilot study. The power is calculated in R based on a two-sample T-test model with
279 our primary outcome, the percent of daily sedentary time assessed using an activPAL. We
280 expected a similar baseline sedentary sample to the study by Falk et al., where participants were
281 sedentary an average of $50.6\% \pm 14.0\%$ of their time [11]. Our proposed sample size of 80
282 participants (40 per group) will allow us to detect a minimum detectable difference of 10.0%
283 between the two groups (i.e., the group difference in averaged sedentary time/total valid awake
284 time) at week 4 post intervention with a common standard deviation of 14.0% with 80% power
285 and a two-sided alpha of 0.05, with 20% drop-out rate accounted. We expect that the ratio of
286 sedentary time/total valid awake time in the self-affirmation + positive framing group will be
287 10.0% less than the control negative framing group, based on our power analysis.

288 After compiling all data across the 3 different data servers, data will be checked for
289 completeness and correctness using frequency distributions (for missing data and out-of-range
290 values). Group differences at baseline are examined for variables including demographic factors
291 (i.e., age, sex, educational level, socioeconomic status, race/ethnicity), baseline sedentary time,
292 self-report sitting time, in order to detect potential confounding factors. For the primary
293 hypothesis that self-affirmation + gain-framed messages decrease sedentary time more so than
294 loss-framed messages, and the secondary outcome of increased MVPA after the intervention, all
295 outcome measures about sedentary behavior and MVPA are first quantified using available
296 software. Changes in sedentary behavior (% daily sitting and lying time, minutes/per day in

297 physical activity) over time (3 time points) are analyzed using linear mixed effect models to
298 account for the correlated data and likely heterogeneous variability. These models will include a
299 random intercept and slope to account for subject-specific changes as well as a group (2) x time

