300 (3) interaction fixed effect. This allows for modelling of the effect of our intervention as a
301 function of both group and time as well as accounting for potential confounding covariates. All
302 model assumptions will be tested both visually and formally and associations between covariates
303 will be assessed to protect against multicollinearity. All valid data are included in the model
304 initially, followed by per protocol analyses, in which the cases with (1) less than 4 valid days of
305 ActiGraph or (2) less than 5 valid days of activPAL or (3) more than 2 days with non-
306 compliance of daily message intervention are excluded in the analysis. For the final dataset, the
307 multiple imputation by chained equations (MICE) will be used for imputing missing values with
308 10 imputations.

309

310 Discussion

311

312 Efficacious behavioral interventions to decrease sedentary behaviors in older adults will
313 have a critical impact on disease prevention, quality of life and public health. The COVID-19
314 pandemic has further heightened the urgency to reduce sedentary due to increased inactivity
315 among older adults [3]. We have designed a 6-week pilot randomized controlled trial to examine
316 the efficacy of daily self-affirmation and gain-framed messaging in decreasing sedentary time.
317 Through increasing receptivity to health messages via reinforcement of self-referential and
318 positive valuation networks, we hypothesize there will be a significant reduction in sedentary
319 time in the intervention group, compared to the control group (who receives loss-framed
320 messages only).

321 There are several notable limitations to this study, yet we have taken a number of
322 measures to minimize their impact. First, this is a pilot study with only a moderate sample size.
323 Nevertheless, a power analysis of our primary outcome measure was performed to ensure that a
324 sample size of 80 is sufficient to detect a true effect with 80% power. Additionally,
325 interpretations of individual component contributions of our intervention are to be taken with
326 caution given we cannot disentangle the effect of gain-framed messaging from self-affirmation.
327 Regarding the inclinometer and accelerometer-based assessments, we are limited to the
328 collection of data for 3 periods of 1 week (i.e., not assessing accelerometry throughout the entire

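### The per-protocol exclusions are not tied to an outcome, so a shortfall on the wrist ActiGraph removes valid activPAL data from the sedentary-time analysis, and the reverse for MVPA

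*SAP*

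**What the plan says.** The SAP's Analysis plan fits the mixed model to all valid data and then narrows the data: "initially, followed by per protocol analyses, in which the cases with (1) less than 4 valid days of" "ActiGraph or (2) less than 5 valid days of activPAL or (3) more than 2 days with non" (the last word is non-compliance, broken at a line end, and refers to the daily messages). One list of exclusions serves both sedentary time and MVPA. *Cases* is not defined as a person or a person-week.

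The two devices have separate jobs. In Physical activity monitoring: "Time spent sedentary as the primary outcome will be measured with an activPAL". The power paragraph agrees: "our primary outcome, the percent of daily sedentary time assessed using an activPAL". The wrist device has a different role: "activity engagement will be measured as secondary outcomes using an GT9X Link". The same section gives each device its own minimum wear: 4 valid days for the ActiGraph, and for the thigh monitor "ActivPAL can reliably estimate sedentary time based on a minimum of 5 days of wear [33]. The".

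Message non-compliance is defined under Daily messaging as no "response to the survey questions or responses under 3 seconds to the self-affirmation probe are" counted as such. That section also says that controls "receive daily prompts to reflect on an everyday activity (e.g., think of a time when you charge" a phone. The Protocol's Daily Messaging section instead gives controls a prompt on their lowest-ranked value, and the SAP Abstract describes control as loss-framed messages only. The legend to SAP Figure 2 puts the messaging period at 42 days and, in the same phrase, at 4 weeks.

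**The concern.** The SAP has a reliability threshold for each device but pools both into one exclusion rule. A participant whose activPAL record meets the SAP's own standard still leaves the per-protocol analysis of the primary outcome if the wrist device recorded too few days. That device contributes nothing to the outcome being analysed. MVPA has the mirror-image problem. Usable data are lost for no gain in validity, from a trial sized with little to spare.

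The compliance limb is a smaller, related problem. Its response-time test is named after the intervention arm's task, so two programmers could build different per-protocol sets. If one applied the test in the intervention arm only, the arms would be screened unequally.

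**Working it through.** **1. The rule applied to single records.**
- 7 valid activPAL days and 3 valid ActiGraph days: the activPAL limb is passed (7 ≥ 5) and the ActiGraph limb is failed (3 < 4). The case is excluded from sedentary time although its activPAL record is adequate.
- 4 valid activPAL days and 7 valid ActiGraph days: the activPAL limb is failed (4 < 5). The case is excluded from MVPA although its ActiGraph record is adequate.

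**2. The plan's sample size.** Inputs from the SAP's Analysis plan: difference 10.0 points, SD 14.0, two-sided alpha 0.05, power 80%, dropout 20%, 40 per group. For a two-sample t-test, the noncentrality is 10 / (14 × √(2/n)) with 2n − 2 degrees of freedom. At n = 32 it is 10 / (14 × 0.25) = 2.857 on 62 degrees of freedom, and power is 80.3%. No smaller n reaches 80%. Then 32 / (1 − 0.20) = 40 per group, so N = 80 is reproduced.

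**3. Further loss through the ActiGraph limb alone.** The documents give no failure rate, so the loss is an assumed range. It is taken from the 32 completers per group (all with valid activPAL data), equally in both arms, and n is rounded down.

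| Further loss | n per group | Power for 10 points | Detectable difference at 80% power |
|---|---|---|---|
| 0% | 32 | 80.3% | 9.96 points |
| 5% | 30 (32 × 0.95 = 30.4) | 77.7% | 10.3 |
| 10% | 28 (28.8) | 74.7% | 10.7 |
| 15% | 27 (27.2) | 73.1% | 10.9 |
| 20% | 25 (25.6) | 69.7% | 11.3 |

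Using only the activPAL limb for the activPAL outcome restores the first row.

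**4. The response-time test.** Exclusion requires 3 or more non-compliant days. With independent days, its probability is the binomial P(X ≥ 3) over 28 or 42 days. Assume the same daily non-response p in both arms and a fast-response rate f that counts in the intervention arm only. The daily probability is then p in control and p + (1 − p)f in intervention.
- p = 2%, f = 2%: intervention 0.02 + 0.98 × 0.02 = 3.96% a day. Excluded, control versus intervention: 1.8% versus 9.8% (28 days), 5.2% versus 23.1% (42 days).
- p = 5%, f = 5%: intervention 0.05 + 0.95 × 0.05 = 9.75% a day. Excluded: 16.3% versus 52.3% (28 days), 35.1% versus 79.0% (42 days).

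If the test covers each arm's own prompt and fast-response rates are equal, the gap between arms is zero.

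**5. Programme length.** Two days are 2/28 = 7.1% of a 28-day programme and 2/42 = 4.8% of a 42-day one. At a 5% daily rate the same limit excludes 16.3% or 35.1%. These rates belong to two programme lengths, not to the two arms.

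**The case against.** The strongest reply is about scope. All valid data are modelled before any exclusion, so a participant with a good activPAL record and a failed ActiGraph stays in that analysis. This is correct, and it confines the point to the per-protocol analyses. A single set of people who adhered to every procedure is also a recognisable choice, but the SAP does not give that as its reason, and its own per-device thresholds point the other way.

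The loss may also be small. The devices are worn together with the same calls and reminders, and the Protocol's Accelerometry section allows extra wear days during the intervention. One might compound a weekly failure rate over three wear weeks to reach a large share of participants. That needs independent failures and removal of the whole person after one bad week, and the documents establish neither.

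A reader might infer from the label that only the intervention arm receives a probe. The documents do not support this. The SAP and the Protocol, in their Daily Messaging sections, both give controls a daily reflection prompt. Both also use a single self-affirmation label for the daily content of the two arms, and non-response counts in either arm. The wording is ambiguous; a one-arm test is not shown.

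A reader might also infer a spurious treatment effect of some stated size. No adherence rates are given, so none can be derived. The planned contrast is group by time, so selection on a participant's stable sedentary level would largely cancel. Bias would need adherence to be related to change, on which the documents are silent.

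**Conclusion.** The point holds for the per-protocol analyses. As written, the rule discards valid activPAL data from sedentary time and valid ActiGraph data from MVPA because of the other device. For an assumed further loss of 5-20% of completers, per-protocol power falls from about 80% to about 78-70%, and the detectable difference rises from 9.96 to between 10.3 and 11.3 points. These figures use the SAP's t-test planning model, assume that dropout has used up the 20% allowance, and ignore losses from the other two limbs. The planned mixed model may differ somewhat.

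The response-time test and the 2-day limit are under-specified. Unequal exclusion would follow only from a literal one-arm application, and no bias in the treatment effect has been shown. The all-valid-data model stands. One loose end is that the Analysis plan imputes a final dataset without defining it, so it is unclear whether excluded cases would be imputed. The rule should be corrected before analysis, but it does not threaten the trial's main estimate.

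**What to change.** In the SAP's Analysis plan:
- Replace the pooled rule with validity by device and outcome, judged per wear week: at least 5 valid activPAL days for sedentary time and at least 4 valid ActiGraph days for MVPA. These are the SAP's own thresholds.
- Define *cases*, and say which dataset is imputed.

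In Daily messaging:
- State that the under-3-second test applies identically to each arm's own reflection prompt, alongside the non-response criterion.
- Reconcile the descriptions of the control prompt across the SAP Abstract, SAP Daily messaging and Protocol Daily Messaging.
- Reconcile the 42-day and 4-week lengths, then confirm the 2-day limit against the settled number of message days.

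The cost is a few sentences and a few lines of code. No new data are needed, and the all-valid-data model does not change.
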